Three groups will be tested: (1) alcohol retrieval / alcohol extinction will be compared to (2) soft-drink retrieval / alcohol extinction and (3) alcohol retrieval / soft-drink extinction. Before and after retrieval-extinction, participants will be tested for alcohol craving and cue-induced physiological responses in laboratory sessions. Retrieval-extinction will be followed by 1 week of “follow-up” GMA reporting, with telephone contact 30 days thereafter.

Outcome parameters: The co-primary outcome measures are: self-reported alcohol craving in the laboratory sessions before and after retrieval-extinction, and GMA reports of alcohol craving and drinking. Daily-life responses are important because the version of retrieval-extinction we will be using, with retrieval induced by drinking alcohol itself, rather than alcohol cues alone, may be especially likely to have effects that generalize from the laboratory to daily life. Secondary outcome measures are: (1) self-reported alcohol craving and drinking at 30-day follow-up, (2) physiological reactivity during sessions, and (3) urine biomarkers for alcohol consumption.

Abbreviated Title: Lab/GMA drinking

Version Date: 2/16/2022

B. Table of Contents

A. Précis.....	2
B. Table of Contents	3
C. Background	5
D. Study Objectives	11
E. Study Design and Methods	12
1. Study overview	12
2. Study procedures.....	13
3. Follow-up/termination procedures.....	26
F. Inclusion and Exclusion Criteria	26
1. Inclusion criteria	27
2. Exclusion criteria	28
G. Clinical and Laboratory Methods	29
H. Collection and Storage of Human Specimens or Data.....	29
I. Statistical Analysis	30
1. Outcome measures	30
2. Analysis of study outcomes	30
3. Criteria for significance	32
J. Required Sample Size	32
K. Plans for Enrollment at Multiple Sites.....	32
L. Human Subjects Protection Plan	33
1. The responsibilities of investigators	33
2. The names of investigators who will obtain informed consent.....	33
3. Rationale for subject selection based on gender/ethnic/race categories at risk	33
4. Recruitment plan	34
5. Justification for exclusion of vulnerable populations	36
6. Evaluation of Risks/Discomforts and Benefits ratio.....	36
7. Subject monitoring	39
8. Conflicts of interest.....	40
M. Protection of Participants' Privacy and Confidentiality.....	40
N. Study Agents/Interventions.....	42
O. Plan for Reporting Unanticipated Problems and Adverse Events	42
P. Data and Safety Monitoring	42
Q. Clinical Monitoring Plan	43

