We have also successfully combined EMA with geolocation information obtained from the global positioning system (GPS) to perform geographical momentary assessment (GMA) (e.g., Epstein et al., 2014). Using GMA, we have shown significant associations between drug craving and independently collected objective measures of neighborhood disorder and drug activity in the Baltimore city locations participants were moving through (Epstein et al., 2014). In the current study, we propose to use GMA because participants' mood and behavior can be readily compared to objective information about alcohol availability (e.g., the addresses of businesses with liquor permits) (Freisthler et al., 2014). Laboratory studies have shown that information about the availability of alcohol significantly affects cue-induced alcohol craving, although both more (MacKillop & Lisman, 2005) and less (Papachristou et al., 2012) craving has been observed when alcohol is unavailable vs. available.

Previously, we have used two separate devices, one for EMA and another for GPS data collection. We currently propose to use a single device, a smartphone, to collect both EMA and GPS data. GPS receiver chipsets have become ubiquitous in smartphones and, by combining GPS information

Abbreviated Title: Lab/GMA drinking

Version Date: 2/16/2022

with information on the strength of signals obtained from cellular data networks and wireless internet data connections (i.e., assisted GPS), smartphones can provide accurate location information more quickly than standalone GPS units and in cases where GPS signals are attenuated (e.g., indoors, in urban areas with many tall buildings) (Zandbergen, 2009; Zandbergen & Barbeau, 2011).

Physiological responses to alcohol cues

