We will measure EtG and EtS in urine. If new urine biomarkers for ethanol are discovered while we are running the protocol, we may measure those as well. We will also measure other substances in the urine samples (such as creatinine) that provide quality assurance for the biomarker measurements.

D. Study Objectives

The objective of this study is to test a novel behavioral intervention, US memory retrieval-extinction, for efficacy in attenuating cue-induced alcohol craving and drinking in problem drinkers.

Our co-primary objectives are to determine whether the retrieval-extinction procedure reduces (1) self-reported craving in response to alcohol cues presented in the laboratory and (2) EMA reports of alcohol craving and drinking in daily life. We have designated these as co-primary outcomes because laboratory data are more mechanistically informative and field data are more clinically relevant. We will assess self-reported craving during laboratory sessions conducted within and between four retrieval-extinction sessions, and then in tests for Pavlovian renewal and reinstatement that will follow the final retrieval-extinction session. We will assess changes in EMA reports before, between, and after the laboratory sessions. We hypothesize that, compared to the control groups, individuals receiving alcohol US retrieval-extinction will show reductions in craving (and possibly in drinking) over time. If we detect our hypothesized effects on the EMA measures alone, we will consider that sufficient evidence for the efficacy of the procedure. If we detect our hypothesized effects on the laboratory measures alone, we will consider that suggestive of possible efficacy, indicating that the procedure might need to be administered more intensively in future work.

Abbreviated Title: Lab/GMA drinking

Version Date: 2/16/2022

Our secondary objectives are to test the effects of the retrieval-extinction procedure on (1) self-reported alcohol craving and drinking at the 30-day follow-up by telephone, (2) physiological responses to alcohol cues in the laboratory, and (3) biomarkers for alcohol consumption. We hypothesize that, compared to control groups, individuals receiving US retrieval-extinction will: report less alcohol craving and drinking at the 30-day follow-up telephone contact; have a reduction in physiological responses to cues; and have a reduction in biomarkers for alcohol consumption.

E. Study Design and Methods

1. Study overview

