A number of previous human studies have used a fixed dose of alcohol that produces BAC of approximately 0.06-0.07 g/dL. Doses in that range (0.5-0.65 g/kg) are considered "moderate" (Rose et al., 2014). Their effects are detectable by participants (Chutuape & de Wit, 1994; Rose & Duka, 2006) and are rated as "liked" (Chutuape & de Wit, 1994). They have been used successfully in studies of the effects of alcohol priming/preloading on several behavioral and subjective endpoints: hypothetical and

Abbreviated Title: Lab/GMA drinking

Version Date: 2/16/2022

actual alcohol choice (de Wit & Chituape, 1993; Chituape & de Wit, 1994; Rose & Duka, 2006), food consumption (Rose et al., 2015), alcohol craving (see also Rankin et al., 1983; Christiansen et al., 2013; Rose et al., 2014), and cognitive and psychomotor test performance (Fillmore et al., 1998; Fillmore & Rush, 2001; Rose & Duka, 2006; Christiansen et al., 2013; Rose et al., 2014).

Extinction: The extinction procedure will begin 30 min after the end of the retrieval procedure to allow for alcohol absorption and distribution. Our intention is for the extinction procedure to occur when participants have a recent memory of alcohol intoxication, such that the temporal window of reconsolidation for that type of memory is open. Participants will spend the 30-min in the same room, to allow for the initiation of physiological monitoring (described below), and, to fill the time, participants will watch a series of short videos (Schiller et al. 2012). Videos will be drawn from the popular (approx. (3 million subscribers) online science and technology video series SciShow and screened for emotional and drug-use content. Participants may be asked to answer a series of brief, open-ended questions about the videos. The list of videos to be used and the list of questions to be asked are provided in the Appendix. At the end of the 30 min, participants will provide a breath sample for determination of BAC, and then the extinction procedure will begin.

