Approximately 30 days after the final laboratory session, we will call the participant to conduct a timeline follow-back calendar (Sobell et al., 1979; Sobell et al., 1996a) and to administer the Penn Alcohol Craving Scale (Flannery et al., 1999). We will then disclose the design of the study to them, explain which experimental group they were in, and debrief them about their perceptions of the study (e.g., whether they had known that they were in a control group or the intervention group).

Following the experimental debriefing, the participant will be asked to speak to a master's-degree-level counselor about his or her drinking behavior. The counselor will provide advice consistent with participants' AUDIT scores (Babor et al. 2001, p. 20) and, when appropriate, referrals to treatment programs and support groups for alcohol-use disorders.

The same advice will be given to study candidates who score in the same range (8-15) on the AUDIT but who are disqualified from study participation for other reasons, such as not endorsing any AUDIT items beyond the first three. This would be done by screening staff toward the end of screening, rather than in a post-study follow-up.

Physiological monitoring during Session 2-6

We will continuously measure heart rate, blood pressure, skin conductance, and skin temperature during the extinction procedures in Sessions 2-5 and during the tests for renewal and reinstatement in Session 6. We will use these measurements to assess changes in participants' physiological responses to the alcohol and soft-drink cues within and between sessions. Physiological measurements will be obtained using a standard laboratory physiological monitoring system: a BIOPAC or Coulbourn Instruments LabLinc noninvasive blood pressure amplifier with CNAP Monitor arm and finger cuffs plus fingertip-mounted skin temperature and conductance sensors. We have used these systems to measure participants' physiological responses to drug and stress cues (NIDA IRP protocols 020, 475).

Geographical Momentary Assessment (GMA) data collection

GMA data collection will begin with the issuing of a smartphone in Session 1 and conclude at the beginning of Session 6, the final laboratory visit. Before being issued a smartphone, each participant will have an instructional session in which the assessment items and smartphone operation are explained.

EMA Entries

Participants will make the following types of entries:

Event-contingent (EC) entries:

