Stored biological specimens will be kept in a secure freezer in the Archway's NIDA freezer room until they are analyzed (BRC building; room 01B405). Specimens that are not used up in the analyses will be saved, but will not be used for any purpose not described in the protocol without prior IRB approval.

Urine samples will be kept in a secure freezer in the Archway's NIDA freezer room until they are analyzed (BRC building; room 01B405) and tracked by barcode. Those that are not used up in the analyses will be disposed of after the study. They will not be used for any purpose not described in the protocol without prior IRB approval. Any unplanned loss or destruction of the samples will be reported by the PI to the IRB.

I. Statistical Analysis

1. Outcome measures

Primary: (1) self-reported alcohol craving during the laboratory sessions, (2) GMA reports of alcohol craving and drinking.

Secondary: (1) self-reported alcohol craving and drinking at the 30-day follow-up, (2) heart rate during laboratory sessions and GMA collection periods, and (3) biomarkers for drinking, detected in urine samples collected during laboratory sessions.

2. Analysis of study outcomes

There are two ways in which we are performing multiple tests of statistical significance. First, we have two co-primary outcomes: a lab measure and an ambulatory measure. This design is actually conservative, because we will not consider US retrieval-extinction fully successful if it affects only the first outcome (protection from renewal/reinstatement in a lab setting) without affecting the second outcome (changes in daily-life behavior).

Second, we need to compare our experimental group to each of the two control groups—we expect the control groups to be similar to each other. If the experimental group differs from only one of the control groups, we will have to conclude that the effect of US retrieval-extinction did not actually require both retrieval and extinction, and thus worked via some unexpected mechanism. Although we might ultimately need to perform the two comparisons separately to explore unexpected findings, our main planned analysis is a single test of the joint hypothesis that the experimental group differs simultaneously from both control groups.

Our specific tests will be as follows.

Abbreviated Title: *Lab/GMA drinking*

Version Date: 2/16/2022

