Co-primary outcome 2: Reduction of craving and drinking in daily life. This will be analyzed in multilevel models, with the dependent variable operationalized in terms of participants' changes in alcohol craving and alcohol drinking in GMA reports after the four extinction-retrieval sessions, controlling for any preexisting differences. Because we cannot predict the time course of differential changes, our main analyses here will omit GMA data from the period when the four extinction-retrieval sessions are occurring. The dependent variable will be daily frequency of craving reports (or, in a separate analysis, daily number of drinks); the independent variables will be coded the same way as in the models for co-primary outcome 1, with experimental group (3 levels) dummy-coded so the experimental group is the reference level and a Wald test of joint significance can assess whether the experimental group differs simultaneously from both control groups. The continuous covariate will be each participant's overall frequency of craving or drinking during the baseline week of GMA.

Depending on the distribution of the dependent variable, we will use either general linear mixed models (e.g., SAS Proc Mixed) or generalized linear mixed models (e.g., SAS Proc Glimmix or SAS Proc NLMixed)—each of which provides a repeated-measures analysis that can handle missing days or early dropout and can accommodate person-level covariates, which will be included if they improve the fit of the model. These models use maximum-likelihood estimation and allow for specification of an

Abbreviated Title: Lab/GMA drinking

Version Date: 2/16/2022

autoregressive error structure (which can be tested against alternative error structures to provide the best-fitting model). In supplementary analyses, we will examine the time course of any differences that emerge during the period when the four extinction-retrieval sessions are occurring.

Secondary outcomes: Most of the other laboratory measures, such as self-reported craving and drinking at the 30-day follow-up visit, urine biomarkers for drinking, and heart-rate responses to cues, will be analyzed by an ANCOVA approach similar to the one used for the co-primary outcome measure 1. Analysis of the GPS component of the GMA data will be more exploratory, but will include testing for group differences in susceptibility to alcohol craving as a function of nearness to bars and liquor stores—a possible reflection of cue reactivity.

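### Heart rate during GMA has no described data source, and laboratory heart rate has no sober pre-treatment value, so a prior-session covariate could bias the control group A contrast

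*Combined protocol and SAP*

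**What the plan says.** **Outcome definition.** Section I.1 gives the second secondary outcome as "heart rate during laboratory sessions and GMA collection periods". The Précis words the same item as "2) physiological reactivity during sessions", and section D as "2) physiological responses to alcohol cues in the laboratory". Neither mentions GMA.

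**Recording.** For GMA, section C says the team will "use a single device, a smartphone, to collect both EMA and GPS data". The part of section E.2 on physiological monitoring lists heart rate, blood pressure, skin conductance and skin temperature. They are taken with a laboratory system using arm and finger cuffs and fingertip sensors, "during the extinction procedures in Sessions 2-5 and during the tests for renewal and reinstatement in Session 6". The stated purpose includes comparing responses from one session to another as well as inside a session.

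**Timing.** The Précis states: "Before and after retrieval-extinction, participants will be tested for alcohol craving and cue-induced physiological responses in laboratory sessions". For Sessions 2-5, section E.2.b places the start of recording in the wait after the beverage is finished: "Participants will spend the 30-min in the same room, to allow for the initiation of physiological monitoring".

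**Analysis.** Section I.2 says that "heart-rate responses to cues, will be analyzed by an ANCOVA approach similar to the one used for the co-primary outcome measure 1". In that co-primary model the outcome is a Session 6 within-session score, and the covariate is each participant's average craving over the earlier sessions.

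**The concern.** Two things do not fit together. First, one part of a listed outcome has no instrument to produce it. Second, the plan announces a physiological test before treatment, but every recording before Session 6 is made after randomised treatment has begun, and after a drink that contains alcohol in two arms and none in the third.

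Section D hypothesises a smaller physiological response to cues in the experimental arm. If Session 2-5 heart rate serves as the baseline or covariate, the acute effect of alcohol enters the comparison with control group A and could be read as a treatment effect. Craving does not have this gap: it is rated before the beverage in each retrieval session, after an entry BAC check of 0.00.

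**Working it through.** **1. GMA heart rate.** The GMA period runs from Session 1 to the start of Session 6. The device is a smartphone that collects EMA entries and GPS. The only heart-rate equipment described is the laboratory system. Section I.2 plans an analysis of heart-rate responses to cues and none of ambulatory heart rate. The GMA part of the outcome therefore has neither a data source nor an analysis. The appendices are not in the text available to me, but sections C and E are explicit about the device.

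**2. What is recorded in the laboratory, by arm (sections E.1 and E.2).**

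| Session | Recording starts | Experimental | Control A | Control B |
|---|---|---|---|---|
| 1 | none | – | – | – |
| 2-5, extinction | after the beverage | target BAC 0.06 ± 0.01; alcohol script | BAC 0; alcohol script | target BAC 0.06 ± 0.01; alcohol-unrelated script |
| 6, renewal | 10 min before cues, each room | entry BAC 0.00, no beverage | same | same |
| 6, reinstatement | before either beverage | both beverages | same | same |

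No arm has a sober value before treatment.

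**3. BAC over the Session 2-5 window.** The plan's own window length reproduces: five 5-min blocks, four 5-min gaps and 20 min of rest give 5×5 + 4×5 + 20 = 65 min. Starting from 0.06 g/dL:
- at the upper elimination rate quoted in section C (30 mg/dL/h), 0.06 − 0.030 × 65/60 = 0.0275 g/dL;
- at an assumed 0.015 g/dL/h, 0.06 − 0.015 × 65/60 = 0.044 g/dL.

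Control group A stays at 0. The gap narrows over the window but does not close.

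**4. Effect on a Session 6 ANCOVA.** Suppose there is no true Session 6 difference, the covariate is the Session 2-5 mean, and alcohol moves that covariate by *s* in the experimental arm and control group B only. With slope β of the Session 6 score on the covariate:
- adjusted control A minus experimental = β × *s*;
- adjusted control B minus experimental = 0, because both are shifted equally.

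The documents give neither *s* nor β, so both are assumed here. With 25 per arm, unit variances (so β equals the correlation) and 2,000 simulated trials per cell, each cell shows the bias β × *s* in SD and, after the semicolon, the rejection rate of the joint two-parameter group test at nominal 5%:

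| *s* (SD) | β = 0.3 | β = 0.5 | β = 0.7 |
|---|---|---|---|
| 0 | 0; 4.7% | 0; 5.1% | 0; 4.9% |
| 0.25 | 0.075; 5.0% | 0.125; 7.4% | 0.175; 12.0% |
| 0.5 | 0.15; 7.9% | 0.25; 16.4% | 0.35; 37.2% |
| 1.0 | 0.30; 17.2% | 0.50; 45.0% | 0.70; 90.4% |

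**5. When it vanishes.** At β = 0 the bias is 0 × *s* = 0 for any shift. A Session 6 difference of within-session changes may depend only weakly on the earlier mean level, and then the true position lies left of the table's first column.

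**The case against.** **The laboratory outcome is derivable.** This stands. Heart rate is recorded in all three arms, a change from pre-cue to cue can be formed because recording begins before the first cue block, and Session 6 treats the arms alike. A reader might infer that the whole outcome cannot be computed. That is true only of the GMA part.

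**The bias is hypothetical.** This largely stands. Section I.2 says only that the approach is similar to co-primary outcome 1 and does not name the heart-rate covariate. A constant shift in level also cancels from a change score. A reader might take a cell of the table as the trial's false-positive rate, but the documents supply no shift or slope to support that. Even so, the prior-session mean is the natural reading of the reference to co-primary outcome 1, section E.2 plans comparisons between sessions, and BAC is not constant over the window.

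**The design covers alcohol exposure.** Control group B is there to control for drinking alcohol in the laboratory, and section I.2 would read a difference from only one control as an unexpected mechanism. This limits the damage. However, the main planned analysis is one joint test, and the table shows that a disturbance confined to the control group A contrast can raise its rejection rate.

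**Two further inferences fail.** A reader might treat experimental versus control group B as the clean comparison in Sessions 2-5 because both drank alcohol. Their scripts differ, so cue type replaces BAC as the confound. A reader might also infer that section I.1 drops three outcomes promised in the Précis and Objectives. Those sections speak of physiology in general and do not name blood pressure, skin conductance or skin temperature. The plan simply leaves the status of those three signals unstated.

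**Conclusion.** The point holds in this form and should be corrected. It concerns one of three secondary outcomes and leaves the co-primary outcomes untouched.

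- **Certain from the text:** GMA heart rate has no described source and conflicts with the Précis, section D and section I.2. No sober pre-treatment physiology is collected, so the Précis statement about testing before treatment is not met. Session 2-5 recordings differ in BAC between control group A and the other two arms.
- **Conditional:** if the ANCOVA adjusts for the prior-session mean, the covariate is post-randomisation and shifted by acute alcohol in two arms. The control group A contrast can then be biased by β × *s*. The size and sign cannot be obtained from the documents. The bias may be small for a within-session change score and is zero if β is zero. The 0.075 to 0.70 SD range rests wholly on assumed shifts of 0.25-1.0 SD and slopes of 0.3-0.7.

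**What to change.** 1. In section I.1, strike the words that extend the heart-rate outcome to GMA periods.
2. Define the outcome as the Session 6 within-session cue response, built like co-primary outcome 1. For renewal, take the change from the 10-min pre-cue recording in the discordant room minus that in the concordant room. Analyse reinstatement separately. Label the other three signals supportive.
3. Do not use Session 2-5 heart rate as the covariate. Start the existing recorder before the Session 2 beverage and use that sober value. Where it was not recorded, leave the covariate out.
4. Report Session 2-5 physiology between arms as descriptive only: control group A differs in BAC, and control group B differs in cue type.
5. Correct the Précis sentence on testing before treatment.

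The cost is wording in sections A and I, plus a few minutes of earlier recording in one session on equipment already in use. The drawback is that the new covariate is a resting value and not a cue response, so it may explain little variance. Items 1, 2, 4 and 5 can be settled before analysis even if Session 2 can no longer be changed.

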Co-primary outcome 1: Protection from renewal/reinstatement of craving in session 6. We will analyze this in a linear regression model so we can control for a continuous covariate: each participant's mean level of craving in prior sessions (along with any person-level covariates that improve the fit of the model). To test the joint hypothesis that the extinction-retrieval group differs simultaneously from both control groups, we will dummy-code the 3-level predictor Group using two variables: Control Group A (0,1) and Control Group B (0,1), thereby making our intervention group the reference level. We will then perform a Wald test of the joint significance of the two Control Group predictors, maintaining an alpha of .05.

The dependent variable will be operationalized in terms of participants' ratings of alcohol craving in the renewal procedure and the reinstatement procedure from session 6. For each participant, we will generate a summary measure of renewal susceptibility (or, for separate analyses, reinstatement susceptibility) using within-session scores from session 6. For renewal, the score will be calculated as:

(pre-to-post-cue craving change in discordant room) *minus*
 (pre-to-post-cue craving change in concordant room)

For reinstatement, the score will be calculated as:

(pre-to-post-cue craving change after alcohol) *minus*
 (pre-to-post-cue craving change after soft drink)

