3. Criteria for significance

Findings will be considered statistically significant at $p \leq .05$, two-tailed, with trends noted at $p \leq .10$.

J. Required Sample Size

We checked prior human studies to find likely effect sizes. For subjective drug craving, the difference between retrieval-extinction participants and control participants had a Cohen d of 1.12 (Xue et al., 2012, figure 3b, change scores for craving on day 4). In a prior human study on reinstatement of physiological reactivity to an extinguished (fear) cue, the difference between retrieval-extinction participants and control participants had a Cohen d of 1.11 (Liu et al., 2014, figure 1). These are large effects. We are powering our study for detection of effects that might be smaller. We used the module “Linear multiple regression: R-squared increase” in G*Power to determine what we could achieve with a realistic sample size. With evaluable data from 75 participants (25 in each of our 3 groups), we will have power of .80 to detect a Cohen f^2 as small as 0.13 on a test of the joint hypothesis that the intervention group differs simultaneously from both control groups in a linear regression model that also contains a covariate for baseline, at a two-tailed alpha of .05. An f^2 of .13 is approximately equivalent to a Cohen d of .61—conventionally considered a medium-sized effect. Despite the large effects seen in the prior studies, we think it is prudent to have power to detect a medium one.

Participants who drop out or are withdrawn from the study will be replaced. We anticipate that we will need to enroll 100 participants in order to have 75 complete the study.

K. Plans for Enrollment at Multiple Sites

Not applicable.

Abbreviated Title: Lab/GMA drinking

Version Date: 2/16/2022

L. Human Subjects Protection Plan

1. The responsibilities of investigators

Responsibilities and qualifications of investigators are given in the protocol appendix.

2. The names of investigators who will obtain informed consent

- [name].
- [name], MSc
- [name].
- [name].
- [name], MS
- [name]
- [name]

Non-FTE staff members will explain the consent form to participants under the direct supervision of a federal employee (FTE) who will sign the consent form.

3. Rationale for subject selection based on gender/ethnic/race categories at risk

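### The multiplicity argument covers only a laboratory-only result; the two EMA variables each have a .05 test, and no rule says whether one or both must succeed for an efficacy claim

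*Combined protocol and SAP*

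**What the plan says.** Section I.2 identifies two sources of multiple testing: the laboratory and ambulatory co-primary outcomes, and the two control groups. The control groups are combined in one joint test per dependent variable: "We will then perform a Wald test of the joint significance of the two Control Group predictors, maintaining an alpha of .05". On the two co-primaries, the plan says: "This design is actually conservative, because we will not consider US retrieval-extinction fully successful if it affects only the first outcome".

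Section D gives the decision rule. "If we detect our hypothesized effects on the EMA measures alone, we will consider that sufficient evidence for the efficacy of the procedure". It treats effects on the laboratory measures alone as merely suggestive.

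Each co-primary outcome has two dependent variables, analysed separately. For co-primary outcome 2, Section I.2 says: "The dependent variable will be daily frequency of craving reports (or, in a separate analysis, daily number of drinks". For co-primary outcome 1, the summary score is renewal susceptibility, "or, for separate analyses, reinstatement susceptibility". Section I.3 sets a single two-tailed .05 criterion for all findings. The plan gives no adjustment or order for the two variables within a co-primary, and no rule for a split between them.

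**The concern.** The account of multiplicity omits a third source, the pair of variables inside each co-primary outcome. This matters most for EMA, because that is the only route by which the trial can claim efficacy. The sentence offered as reassurance concerns a laboratory effect without a daily-life effect. It does not address a craving effect without a drinking effect, or the reverse.

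If a significant result on either EMA variable would be reported as evidence of efficacy, the 5% level applies to each test but not to the claim. The choice of which variable decides could also be made after the results are known. The study is unblinded and these outcomes are self-reported, so the decision rule should be fixed in advance.

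**Working it through.** **Inputs from the plan.** Alpha is .05 per joint test (Section I.2, co-primary outcome 1; Section I.3 for all findings). Section J gives the sample size: "With evaluable data from 75 participants (25 in each of our 3 groups". It gives the power: "we will have power of .80 to detect a Cohen f^2 as small as 0.13", for a joint test of two group terms in a model with one baseline covariate, "at a two-tailed alpha of .05". Section P rules out interim analyses, so no alpha is spent there. The correlation between EMA craving and drinking is not given; I assume a range from 0 to .9.

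**The plan's own figure.** Numerator df = 2; denominator df = 75 − 3 − 1 = 71; noncentrality = .13 × 75 = 9.75. Noncentral F gives power .787 at f² = .13, and .80 at f² = .134, which rounds to .13. The stated power is reproduced. It applies to one joint test, not to a pair.

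**EMA pair, if either variable suffices.**
- Independent tests: 1 − (1 − .05)² = .0975.
- Upper bound under any dependence: .05 + .05 = .10.
- Correlated outcomes, by simulation under the complete null (three groups of 25, F on 2 and 71 df, 200,000 replicates, simulation error about .001):

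| Assumed correlation | At least one rejection |
|---|---|
| .3 | .096 |
| .5 | .092 |
| .7 | .086 |
| .9 | .072 |

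This is about 1.4 to 1.95 times .05.

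**EMA pair, other rules.** If both tests must be significant, the rate is .05² = .0025 under independence and about .029 at a correlation of .9. If craving must be significant, whatever happens to drinking, the rate is at most .05. Neither rule inflates the error.

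**Direction.** The joint test is non-directional, but Section D hypothesises reductions relative to the controls. Under the null each of the three groups is equally likely to be lowest, so one test rejects with the experimental group lowest at a rate of .05 / 3 = .0167. For two independent tests, 1 − (1 − .0167)² = .033; simulation gives about .031 at a correlation of .5.

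**All four co-primary tests.** Any positive result: 1 − .95⁴ = .185 if independent, with an upper bound of .20; about .160 at a common correlation of .5 and .096 at .9. This is the chance of some positive co-primary finding, not of an efficacy claim.

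**Power at an adjusted level.** At alpha .025 and f² = .13, power is .69, against .787 at .05. The planned EMA model is multilevel, so these linear-regression powers are approximate for EMA.

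**The case against.** The best defence is that Sections D and I.2 are consistent. A reader might infer that one requires both co-primaries and the other does not, but Section I.2 says only that a laboratory-only effect falls short of full success, and Section D says the same in other words. Under that rule, adding the laboratory outcome creates no extra chance of claiming efficacy. This stands: there is no contradiction, and the laboratory tests do not inflate the efficacy error.

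A second point also stands. The plan never says that either EMA variable is enough. Section D speaks of the EMA measures in the plural, and its hypothesis is firm for craving but treats drinking only as a possibility. That leans towards craving as the deciding variable, in which case nothing is inflated. But it is a lean, not a rule. Drinking is listed within a primary outcome, and nothing excludes a claim based on drinking alone.

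Third, once direction is considered, the absolute chance of a false efficacy claim is below 5% even for the pair. That is correct under the complete null, though the near-doubling relative to a single test remains. The plan's stated criterion is the two-tailed .05, not this directional one.

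None of this supplies a rule for a split between the two EMA variables.

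**Conclusion.** The concern holds in limited form. The conservative label does not protect the efficacy claim from the two EMA tests, and the plan leaves open how they combine. If either suffices, the error rate of the non-directional tests is at most about .0975, and lower with correlation; in the hypothesised direction it is about 3.3% instead of 1.7%. These figures rest on the either-suffices reading, the complete null and assumed correlations. If craving or both were required, the problem disappears.

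A reader might infer that the false-positive rate for efficacy is doubled or worse, or that the four-test figure of about .185 measures it. The documents do not support this. Doubling is the ceiling for the EMA pair, and Section D says laboratory effects alone are only suggestive. The point is worth correcting because the decision rule is undefined and cheap to define; it does not invalidate the design.

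**What to change.** In Section I.2, remove the statement that the design is conservative as the justification for not adjusting, and list the two variables within each co-primary as a source of multiplicity. Then state the EMA decision rule in one of two ways.

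- **Fixed sequence.** Daily craving-report frequency is the deciding EMA test at .05, in line with the emphasis of Section D's hypothesis. Daily drinks is tested at .05 only if craving succeeds. Craving loses no power. The price is that no confirmatory drinking claim is possible when craving fails.
- **Holm across the two EMA tests.** Either variable can then support efficacy with the familywise error held at .05. Power for a single test is no lower than about .69 at f² = .13 (from .787). This is a floor, because a test is carried out at .05 once the other has been rejected.

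Both are changes of wording. Ordering renewal and reinstatement in the same way is optional; it would tidy the laboratory co-primary but is not needed to protect the efficacy claim.
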